### **10.4 Sample size, accrual rate and study duration**

We plan to accrue approximately 55 patients per year for the first three years of the study; this assumes a 10% dropout rate. The power (97.3%), is based on 150 patients, using a two-sided binomial test at the 5% significance level to detect an increase in the 24-month cumulative progression rate from 12.5%, as expected for AS historically, to 25% for MRI-AS. Enrollment will occur during the first 3.25 years. Enrollment will be completed at < 3.33 years from the enrollment of the last patient.

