Despite a worldwide acceptance of active surveillance in men with low risk tumors, nearly a third of men will progress to requiring treatment within the first three years. Most active surveillance protocols select patients with low volumes of low grade tumor seen on diagnostic biopsy. However, unlike other solid tumors where a lesion is visualized on imaging and a needle is inserted directly into it, most methods of visualizing the prostate cannot reliably identify lesions that are localized to the prostate. As a result, the current standard for diagnosis involves visualizing the prostate via transrectal ultrasound and performing segmented biopsies of the gland for cancer detection because the tumor(s) is not usually identified clearly. Given the heterogeneous nature of prostate cancer, where both indolent and aggressive tumors may be found in the same gland and some tumors are located in regions of the prostate (e.g., anteriorly) not thoroughly sampled, this "sampling" approach may miss the dominant or high grade tumors, which are likely to be the drivers of progression.

This is confirmed by a 20-30% chance of seeing a higher grade or volume of tumor when a second biopsy is performed. Furthermore, data from surgical patients suggest that 20-30% of patients who appear to be good candidates for surveillance may harbor high-risk features within their prostates suggesting that their biopsy may have underestimated the aggressiveness or volume of tumor present. This highlights the need for serial biopsy, but also suggests that those patients who are likely to progress early are not truly progressing, but more likely to harbor higher risk tumors that were missed on initial biopsies; a process referred to as "reclassification". Therefore, men choosing active surveillance must understand that the biopsy may not reflect the true biology of their disease, and there is some inherent risk involved that they may lose their opportunity for cure while their tumor is being monitored.

The primary goal of active surveillance is to monitor tumors that are deemed not to require immediate treatment with the goal of timely intervention at the point of tumor

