## 1.4 Rationale

### 1.4.1 Rationale for Studying Active Surveillance Patients

Radical prostatectomy and radiotherapy, the two most common and potentially curative treatment options for prostate cancer come at a significant impact to health related quality of life. With earlier diagnosis from PSA screening, there may be as much as a 15 year lead time before the majority of patients progress and metastasize. Active surveillance has emerged as an appropriate and safe alternative to immediate treatment and is supported by both the American Urological Association and the European Urological Association. Our center has one of the largest active surveillance cohorts in the world. With a median follow up of 3 years about 30% of patients experienced progression of tumor. However, no patient in our series has developed metastasis or mortality. Given the success and emerging popularity of active surveillance, there is a consideration to expand the criteria for surveillance to allow intermediate risk patients to be considered eligible. However, some patients who undergo delayed surgery after initial surveillance have adverse histological findings that may portend worse outcomes or require further secondary treatments to establish cure. It is likely that many of these patients harbored higher risk disease that was missed on initial evaluation of their prostate. Therefore, any biomarker, predictive tool, or imaging modality that could identify these patients early would be a welcome addition to reduce the likelihood of an adverse outcome due to poor selection of suitable patients.

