## 1.5 Preliminary Studies

### 1.5.1 Experience with active surveillance

The Department of Urology at the University of Miami has a significant experience in active surveillance. Currently the clinical and histological criteria for surveillance include Gleason  $\leq 6$  (3+3), PSA  $\leq 20$ ng/mL, and two or fewer biopsy cores with no more than 20% tumor present in each core. All patients had at least one confirmatory surveillance prostate biopsy. At diagnosis, the mean age of the AS patients was 62 years (range 33-79 years) with a mean PSA of 5.1 ng/mL. The mean follow-up for the cohort was 2.9 years (interquartile range (IQR) 1.4-24.0 years). On the first re-biopsy, 52% of the patients had no tumor. Only 7% of the AS patients had tumor progression (to some component of Gleason 4 disease) on first re-biopsy. In the second and third surveillance biopsies, 18% and 17% of the patients respectively progressed. Of the 249 men in the AS cohort as of this analysis in 2011, 64 (26%) demonstrated biopsy progression and 61 of them have been treated. No patient died of prostate cancer. Among the 61 treated patients, 32 had radical prostatectomy, 27 had interstitial or external beam radiation, and for 2 patients the type of treatment was unknown. Three men with an increase in tumor burden in follow-up biopsies elected to continue active surveillance despite the biopsy progression. However, the Miami criteria for active surveillance is very conservative and may exclude many men for whom surveillance would be acceptable. These criteria have been expanded in current clinical practice.

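### The 12.5% historical benchmark for the 24-month cumulative endpoint has no source, equals the mean of two per-biopsy rates, and is probably too low

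*Combined protocol and SAP*

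**What the plan says.** Section 10.4 bases the sample size on a two-sided binomial test at 5% with 150 patients and 97.3% power, "to detect an increase in the 24-month cumulative progression rate from 12.5%, as expected for AS historically, to 25% for MRI-AS". It gives no citation or derivation for 12.5%, and the figure appears nowhere else.

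The centre's own data are in Section 1.5.1. At the first re-biopsy: "Only 7% of the AS patients had tumor progression (to some component of Gleason 4 disease) on first re-biopsy". At the next two: "In the second and third surveillance biopsies, 18% and 17% of the patients respectively progressed". Overall, of 249 men, "64 (26%) demonstrated biopsy progression". On follow-up: "The mean follow-up for the cohort was 2.9 years (interquartile range (IQR) 1.4-24.0 years". On biopsy coverage: "All patients had at least one confirmatory surveillance prostate biopsy". Section 1.4.1 adds: "With a median follow up of 3 years about 30% of patients experienced progression of tumor".

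Section 10.1.1 defines the cumulative rate as progressors divided by men who have had every planned biopsy so far or who progressed earlier. Section 10.5 names the 24-month cumulative rate as the primary endpoint. It also says that groups will be compared by a log-rank test, and does not say which test uses the 12.5%.

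**The concern.** The trial has one arm, so the historical rate is the only yardstick for the primary objective. If the yardstick is too low, the trial can declare that MRI-guided biopsy raised early detection when the observed rate is simply what conventional surveillance would have shown.

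The value invites the question because (7 + 18)/2 = 12.5 exactly. The 7%, 18% and 17% are rates at each successive biopsy. They are not cumulative, because the third is below the second. They are not shares of the whole cohort either, because they sum to 42% against 26% overall. Averaging two such rates gives the mean risk at one biopsy, not the risk accumulated over two.

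**Working it through.** **1. The plan's own figure.** Inputs from Section 10.4: n = 150, p0 = 0.125, p1 = 0.25, two-sided 5%. With the exact binomial, the smallest count with an upper tail of at most 0.025 under p0 is 28 (P(X ≥ 28) = 0.0193). Power is P(X ≥ 28 | 0.25) = 0.9734, so the stated 97.3% reproduces.

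**2. The two per-biopsy rates read cumulatively.** Inputs from Section 1.5.1: 7% and 18%. If every man still at risk had the second re-biopsy, the cumulative rate is 1 − 0.93 × 0.82 = 0.237.

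Let g be the share of at-risk men who had a second re-biopsy by 24 months. The documents do not give it.

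- Section 10.1.1 denominator: (0.07 + 0.93 × 0.18 × g)/(0.07 + 0.93 × g). At g = 1 this is 0.237. At g = 0.329 it is 0.125/0.376 = 0.333. It rises as g falls, so 23.7% is the minimum, taking 7% and 18% as given.
- Whole-cohort denominator: 0.07 + 0.93 × 0.18 × g. This runs from 7% at g = 0 to 23.7% at g = 1. It equals 12.5% at g = (0.125 − 0.07)/(0.93 × 0.18) = 0.329, about 76 of the 232 men still at risk.

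**3. The crude totals scaled to 24 months.**

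- 64/249 = 0.257 at a mean of 2.9 years: linear 0.257 × 2/2.9 = 0.177; constant hazard 1 − (1 − 0.257)^(2/2.9) = 0.185.
- About 30% at a median of 3 years (Section 1.4.1): linear 0.30 × 2/3 = 0.200; constant hazard 1 − 0.70^(2/3) = 0.212.

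These give about 18-21%. They are rough, because the totals are crude proportions, the reported mean and interquartile range of follow-up conflict, and 7% followed by 18% suggests that the hazard may not be constant.

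**4. What the Section 10.4 rule does if the true historical rate is higher.** The third column is the chance of reaching 28 of 150 when MRI adds nothing. The fourth resets the critical value to the null in the first column and gives power for 25%. The last repeats that for 230 × 0.9 = 207 evaluable men (accrual goal in Section 4.1, dropout in Section 10.4).

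| True historical rate | Basis | Chance of declaring an increase, n = 150 | Power for 25%, n = 150 | Power for 25%, n = 207 |
|---|---|---|---|---|
| 12.5% | Section 10.4 | 1.9% | 97% | 99% |
| 13.6% | illustrative | 5% | 94% | 99% |
| 18.5% | 64/249 scaled | 51% | 49% | 57% |
| 20% | 30% scaled, linear | 69% | 28% | 39% |
| 23.7% | two biopsies | 94% | 5% | 6% |

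The upper tail already reaches its nominal 2.5% at a true rate of about 12.8%. With 207 men the corresponding rule for 12.5% rejects at 37 or more. Its chance of a false declaration is about the same at 13.6% (5%) and higher at 18.5%, 20% and 23.7% (62%, 80% and 98%). A larger sample helps power, not this error.

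**The case against.** Five points can fairly be made for the plan.

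- **There is no arithmetic error.** The power calculation is right, and 12.5% is a planning assumption. This stands: the fault lies in an undocumented input.
- **12.5% is not excluded.** With a whole-cohort denominator and about a third of at-risk men re-biopsied a second time by 24 months, the centre's rates give exactly 12.5%. Adding 17% at a third biopsy then gives 1 − 0.875 × 0.83 = 27.4%, close to the reported 26-30%. This also stands. However, that denominator keeps men who missed a biopsy, which Section 10.1.1 does not, so the benchmark and the endpoint would measure different things.
- **The source may not be the Miami series.** Section 3.1 speaks of historical cohorts in the plural. This is why averaging can only be an inference. It does not help the plan, since no other source is named.
- **The populations and definitions differ.** The historical 7% is progression to a Gleason 4 component under narrower entry criteria, while the trial endpoint also counts core numbers and any treatment. This is true, and it limits how firmly any figure above can be carried over.
- **The accrual goal is 230.** Power is then somewhat higher, but the false-positive risk is no lower.

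Stronger readings are tempting and are not supported. A reader might infer that the sponsor did average the two rates, that 12.5% is impossible, or that 23.7% is the correct null. The documents give no derivation, no count of second re-biopsies and no biopsy dates. A reader might also treat a band such as 14-24% as established. Its lower part would rest on guessed biopsy counts and a denominator that the plan does not use, and 23.7% is a minimum on the plan's denominator, not an upper limit. Section 1.1 says that "nearly a third of men will progress to requiring treatment within the first three years", but this describes treatment in other series and does not fix a 24-month value.

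**Conclusion.** The concern holds as one about an unsourced and probably too low benchmark. The direction is well supported: the centre's two rates give at least 23.7% on the trial's own denominator, and its crude totals scale to about 18-21%. The size is of moderate confidence. It rests on taking 7% and 18% as given, on treating the second re-biopsy as falling within 24 months, and on approximate scaling for the lower figures.

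Little error is needed for it to matter. The false-positive chance passes 5% once the true historical rate exceeds about 13.6%, and is roughly 50-94% across 18.5-23.7%. As written, a significant result would not by itself show that MRI increased early detection. Whether the endpoint covers two or three biopsies, and the conflicting follow-up summary, are separate items. The first must be settled before any replacement rate can be matched to the endpoint.

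**What to change.** - **Section 10.4, null.** Replace 12.5% with a cumulative historical rate tabulated from the University of Miami active surveillance database, using the Section 10.1.1 definition and denominator. Match on number of biopsies, 24-month horizon and eligibility as far as the records allow. State the source, n, 95% CI and any remaining mismatch. Adopt none of the values derived here as the null.
- **Section 10.4, alternative and power.** Re-justify 25% against the new null, and restate power at the planned evaluable number over the CI of the tabulated rate.
- **Section 10.5.** Name the primary test that uses the benchmark. If the historical men are to be compared as data and not as a fixed value, base the power on that comparison.

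The cost is one tabulation from a database the site already holds, a rewrite of Section 10.4 and a sentence in Section 10.5. The match may be incomplete, because the historical criteria exclude part of the trial population and the historical biopsy schedule is not stated. A larger sample is not necessarily needed. If the sponsor chose to keep a 12.5-point increase, exact power at n = 150 would be about 95%, 93% and 91% for nulls of 18.5%, 20% and 23.7%, treating the null as known.

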## 10.5 Statistical Analysis

Descriptive statistics will be done for patient demographics and baseline disease characteristics. Counts and percentages will be used to summarize the distribution of categorical variables while median, range, mean and standard deviation will be used for continuous variables. Baseline characteristics will include age, race/ethnicity, T-stage, Gleason score, PSA, PSAD and performance status. Continuous scores will be compared using ANOVA and linear regression controlling for common demographic and clinical variables.

For each scheduled surveillance biopsy session, we will tabulate patients and the following status categories: biopsy indicating progression, biopsy negative for progression, biopsy not performed for progression detected on earlier biopsy, biopsy not performed because patient refused, or biopsy not performed because patient dropped out of study.

Time to event endpoints such as progression and BCR will be analyzed by Kaplan-Meier (KM) or competing risk (CR) methods. Where the Kaplan Meier method is used, point estimates and two-sided 95% confidence intervals for rates will be reported for selected times using Greenwood's variance and the log-log transform method. Median survival time, if attained, will also be reported. We will report the progression rate and the cumulative progression rate for each surveillance biopsy. Taking the third scheduled biopsy at the end of 2 years as illustration, the progression rate at 24 months is the proportion of biopsied patients indicating progression among the total number of biopsied patients over the 24 month period. The 24-month cumulative progression rate is the primary endpoint, which will include those who complete the first three biopsies or have progression from the first or second biopsy. The primary endpoint, 24-month cumulative progression rate, will be estimated and reported with corresponding 95% confidence intervals. Groups will be compared by the log rank test. In addition, we will report and plot the cumulative progression rates in each arm for the four scheduled surveillance biopsies. It is expected that the early difference with historical values and those obtained with MRI-guided biopsies will not be sustained; that is, the 36-month cumulative progression rates will be approximately equal. Similar estimation of time-specific and cumulative rates will be done for Histological progression.

For radiomic signatures, gene signatures, and other biomarkers such as Gleason score and percent positive tissue (PPT), descriptive statistics (counts and percents; median and range; mean and standard distribution) and box plots will be used to summarize the distribution of the variables. In particular, once the habitats are defined, imaging features may be extracted. These features describe characteristics of the image intensity histograms (e.g., high or low intensity), tumor shape (e.g. round or spiculated), texture patterns (e.g. homogeneous or heterogeneous), as well as tumor location. We will consider a two-stage feature selection approach. In the first step, we will filter out "radiomics" variables using standard t-test or ANOVA and in the second step; we will perform random forests to identify radiomics signatures of habitats in relation to risk groups. Genes will be selected using Significance Analysis of Microarray (SAM) in R package, which allow the determination of significantly differentially expressed genes between classes (HP-Risk 1-4) controlling the Benjamini-Hochberg false discovery rate (FDR). The augmented classifiers predictive model will be developed using multivariate ordinal logistic regression. We will use area under the

receiver's operating characteristic curve (AUC) with 10-fold cross-validation approach to evaluate performance of prediction model. Radiomic profiles on multi-parametric MRI that suggest regions of the prostate that are suspicious for more aggressive prostate cancer will be correlated to histopathologic findings from biopsy of these regions. Genomic profiles from tissue cores in each region will be correlated to radiomic profiles and histopathology from that region to see what each adds to improving the ability to predict patients who are likely to harbor more aggressive tumors that would portend poor outcome on active surveillance. Radiomic and genomic profiles from MRI targeted biopsies will be compared to segmental biopsies to see if profiles from targeted biopsies are more informative for risk assessment compared to segmental biopsy using longitudinal analysis approach. We will also assess how these profiles change over time in serial imaging and biopsy and see if/ how these profile changes correlate to change in histopathology. We will also relate genomic and radiomic profiles of the prostate to common serum and urinary markers that have been used predict progression on active surveillance. For continuous outcomes, association between outcome and other covariates will be examined using linear regression model and correlation coefficient. For binary outcomes and time-to-event outcomes, logistic regression and Cox proportional hazards regression will be used, respectively. All tests will be two-sided and statistical significance will be considered when  $p < .05$  after multiplicity adjustment.

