## 2. HYPOTHESES

- 1) Multiparametric MRIus-guided or direct MRI-guided biopsies will allow for more directed sampling of the tumors from compartments with distinct MP-MRI characteristics, termed habitats, that will increase the rate of "progression" on early (first and second) surveillance biopsies and decrease the rate of "progression" on late (third and further) surveillance biopsies compared to historic TRUS-guided biopsy rates.
- 2) Identifying higher risk tumor early on will reduce the proportions of patients with poor response to delayed primary treatment
- 3) Radiomics signatures from MP-MRI will define patterns that are associated with progression
- 4) Genomic signatures based on RNA from tumor tissue will define patterns that are associated with habitats and radiomics signatures, as well as progression.

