#### **3.3 Exploratory Objectives**

- 1) To define radiomic signatures on multiparametric MRI that select regions of the prostate that are likely to harbor more aggressive disease.
- 2) To molecularly characterize tissue from the multiparametric habitat-directed prostate biopsies and develop genomic signatures of indolent versus progressing prostate cancer using a 1.4 million feature oligonucleotide microarray capable of global high throughput analysis of formalin fixed paraffin embedded specimens.
- 3) To relate radiomics and genomics signatures to existing urine, serum and tissue biomarkers that have been associated with prostate cancer diagnosis and/or progression.
- 4) To determine the incremental benefit of mpMRI, genomic risk testing, and molecular markers at baseline compared to NCCN risk class for predicting reclassification on confirmatory baseline biopsy.
- 5) To evaluate serial changes in mpMRI, genomic risk scores and molecular markers and relate them to progression on active surveillance.

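### The genomic signature is meant to separate indolent from progressing cancer, but 10.5 selects genes on a risk class (HP-Risk 1-4), so genes that predict later progression beyond that class would mostly be lost

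*Combined protocol and SAP*

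**What the plan says.** **Aims.** Exploratory objective 2 (3.3) is to "develop genomic signatures of indolent versus progressing prostate cancer". In section 2, hypothesis 4 expects RNA-based patterns "that are associated with habitats and radiomics signatures, as well as progression", and hypothesis 3 reads "Radiomics signatures from MP-MRI will define patterns that are associated with progression". Radiomic exploratory objective 1 (3.3) has a different target: "To define radiomic signatures on multiparametric MRI that select regions of the prostate that are likely to harbor more aggressive disease". Section 1.4.4 expects the radiomic and genomic data to complement histology in picking out men who will do badly on surveillance.

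**Methods (10.5).** Genes are chosen with SAM as the "significantly differentially expressed genes between classes (HP-Risk 1-4"), under false discovery rate control. Radiomic features pass a t-test or ANOVA filter whose grouping variable is not named. The second step uses "random forests to identify radiomics signatures of habitats in relation to risk groups". The combined classifier is an ordinal logistic regression, assessed by AUC with 10-fold cross-validation.

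**Related text.** HP-Risk appears only in that sentence of 10.5 and is not defined. Section 10.3.2 promises a predictive model with 493 genes in 16 pathways and names no outcome for it.

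**The concern.** Progression in this trial (10.1.1, 10.1.2) is an event that happens or does not, or a time to that event. A four-level ordered class is neither. SAM applied to HP-Risk tests whether expression differs between risk classes. It does not test whether expression is related to progression. If HP-Risk reflects the histology of the tissue, as seems likely, the signature will largely restate what the pathologist already reports.

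Objective 2 needs genes that say something about later progression that current risk does not. Such a gene can fail the class-based screen and then never reach a model in which progression is the outcome.

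**Working it through.** **1. Aims against selection labels**

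| Aim | Target | Label used in 10.5 | Match? |
|---|---|---|---|
| Exploratory objective 2 | Indolent or progressing cancer | HP-Risk 1-4, ordinal model | No |
| Hypothesis 4, progression part | Progression | HP-Risk 1-4 | No |
| Hypothesis 4, habitat part | Habitats and radiomics | HP-Risk 1-4 | Plausible |
| Hypothesis 3 | Progression | Risk groups (random forest) | No |
| Exploratory objective 1 | Aggressive regions | Risk groups | Yes |

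**2. The plan's own figure.** None is given for the signatures. The only design figure is in 10.4: 97.3% power with 150 men, 12.5% against 25%, two-sided 5%. The exact binomial test rejects at 28 or more progressors (upper-tail probability 0.0193 at 12.5%). Power at 25% is 0.9734, so the figure is reproduced. It matters here only as the source of n = 150 and the 25% rate.

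**3. Why class selection loses such genes.** Suppose a gene is shifted by d SD in men who progress and has no class effect of its own. Its expected difference between classes j and k is d × (P[progress | j] − P[progress | k]). This is zero if class and progression are unrelated, and otherwise only a fraction of d.

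**4. Size, by simulation.** From the plan: 493 genes, n = 150, 25% progressing. All else is assumed: class mix 45/30/15/10%; 25 genes rising 1.2 SD from class 1 to class 4; 25 genes shifted 0.6-1.0 SD in progressors only; the rest noise; ANOVA with Benjamini-Hochberg at 5% as a stand-in for SAM; 300 runs per setting.

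| Log-odds of progression per class | Progression-only genes kept, selecting on class | Selecting on progression |
|---|---|---|
| 0 | 0.2-0.3% | 45-98% |
| 0.5 | 0.6-1.6% | 47-99% |

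Class selection keeps about 87% of the class-only genes. At n = 75 the recovery of progression-only genes is 0.1-0.3% against 7-68%.

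**5. Stronger link between class and progression.** A second set of assumptions was tried: equal classes, 20 progression genes at 0.8 SD, 20 class genes at 0.4 SD per step.

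| Log-odds per class | 0 | 0.5 | 1.0 | 1.5 | 2.5 |
|---|---|---|---|---|---|
| Progression genes kept, selecting on class | 0.2% | 0.9% | 4.0% | 9.9% | 27.6% |

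Selecting on progression keeps 84-89% throughout.

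**6. Genes carrying both effects.** With a class effect of 1.2 SD plus a progression effect, class selection at n = 150 keeps about 81-98%. With a class effect of only 0.6 SD it keeps about 4% at log-odds 0 and about 18-24% at 0.5.

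**7. Events available to the alternative.** 150 × 0.25 = 37.5 men by 24 months (230 × 0.25 = 57.5 at the accrual goal in 4.1). By 10.5 that rate covers the first three biopsies, so it includes the initial one. The split is not given, so two are assumed:
- Half at the initial biopsy: 37.5 / 2 ≈ 19 events remain among 150 − 19 = 131 men. Recovery of progression-only genes falls to about 12-86%, depending on effect size and varying between runs.
- Two thirds at the initial biopsy: about 12 events remain among 150 − 25 = 125 men. Recovery is about 4-61%.

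The 36-month biopsy would add some events.

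**The case against.** **HP-Risk is undefined.** A reader might infer that the selection label certainly excludes progression. The documents do not show that. What they show is that the label is unexplained and not tied to objective 2. An ordinal model of four classes points to a risk grade, and 10.3.1, which uses biopsy histology to judge habitats, fits that reading. Neither proves it.

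**The radiomic plan is largely consistent.** A reader might extend the criticism to both signatures. Objective 1 seeks aggressive regions, and risk groups serve that. HP-Risk is named only for genes, and the grouping for the radiomic filter is not stated. Only hypothesis 3 carries the point over to imaging.

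**Region-level work needs a region-level label.** Sections 1.5.2 and 10.5 plan to relate habitats to the histology and expression of the same region. Progression belongs to the man and cannot label single regions. This stands, and is a reason to keep the HP-Risk analysis.

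**Progression is analysed elsewhere.** Section 10.2.3 models progression from NCCN class plus mpMRI and genomic scores, 10.3.4 relates serial scores to progression, and 10.5 has a general provision for logistic and Cox models. All true, but these take the scores as given or name no role in feature selection.

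**The loss depends on how genes behave.** A reader might infer that genes foretelling progression are missed in general. That is too strong. Section 1.1 holds that early progression is mostly higher-risk tumour missed at first, and progression is itself defined by Gleason score and core counts. Many relevant genes may therefore differ by class and be kept. A simulation that separates the two kinds of gene shows the worst case.

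**Conclusion.** The mismatch holds for the genomic signature. Objective 2 and the progression part of hypothesis 4 ask about progression, while the only gene-selection step and the classifier are built on a risk class. No section selects features on progression. Hypothesis 3 has the same gap; radiomic objective 1 does not.

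The loss is confined mainly to genes informative beyond the class. Of those with no class effect of their own, roughly 0.2-1.6% are kept when class and progression are weakly linked or unlinked, rising to 27.6% at the strongest link tried. Selecting on progression does better in these settings, but once men who progress at the initial biopsy are set aside its advantage is smaller and uncertain. All these percentages rest on assumed effect sizes, class mixes and timing of events, and on ANOVA standing in for SAM. They show direction and rough size and do not predict a yield.

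A reader might also infer that the plan will present a risk-class signature as one of progression. The documents do not say so; they leave the outcome of the 493-gene model open. The point concerns exploratory work only. The primary endpoint and its power are untouched.

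**What to change.** In 10.5:

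1. Define HP-Risk 1-4: what it is built from, whether it applies to a core, a region or a man, and which objective it serves. Name the grouping variable for the radiomic t-test or ANOVA filter.
2. Keep the HP-Risk and risk-group analyses, under their own label, for the region-level habitat-to-histology work and radiomic objective 1.
3. For objective 2 and the progression part of hypotheses 3 and 4, add feature selection and a logistic or Cox model with histological progression (10.1.2) after the initial protocol biopsy as the response. Use features from the initial biopsy and MRI, one record per man, in men who have not progressed at that biopsy, and adjust for baseline risk class.
4. Repeat feature selection inside each fold of the 10-fold cross-validation, so that the AUC is not inflated by selecting on the held-out men.
5. State in 10.3.2 which outcome the 493-gene model predicts.

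The cost is SAP wording and a further analysis of data already being collected. The drawback is few events: at most about 38 of 150 men by 24 months at the planned rate, and fewer once men progressing at the initial biopsy are excluded. Fewer genes will be declared, power will be modest, and the report should say so.
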